3.1.3 Follow-up Phase

Their initial baseline visit (Visit 1) will occur before clinically prescribed ivacaftor treatment has begun. The exact date of the start of medication will vary for families as they obtain

their medication. Subjects will return to CHOP for the 6 week visit (Visit 2) and the 12 week visit (Visit 3 and final) after subject/family has confirmed the timing of the start of ivacaftor treatment. There may be a delay between the baseline visit and the 6 week visit based upon when treatment begins. For most families, the total duration of the study will be from 4 to 6 months. The duration of the study from start of ivacaftor treatment until last study visit will be 12 weeks. For each of the 6 and 12 week visits following the start of ivacaftor treatment, there will be a window of ±2 weeks for the visit to occur (i.e. 6 week visit may occur between 4 and 8 weeks, and 12 week visit between 10 and 14 weeks post ivacaftor treatment).

Refer to Table 1 for list of assessments and the study timeline for the visit schedule.

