3.2.2 Total Number of Study Sites/Total Number of Subjects Projected

The study will be conducted at one investigative site in the United States.

Recruitment will stop when 18 subjects are enrolled. It is expected that 18 subjects will be enrolled to produce 16 evaluable subjects.

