	Day 3 (if needed and expected for half of subjects)

• Sleeping energy expenditure test- if it was not performed on Day 2

Post Visit Follow Up

- 3-day weighed food records
- Maintain adverse events calendar until 3-day food records are completed

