6.2 Sample Size and Power

Sample Size and Power: This is a longitudinal study of the effects of ivacaftor treatment on outcomes before and after 12-week treatment. The sample size of 16 subjects to complete the study has been determined as adequate to have the power to test the primary outcomes of decrease in SEE percent predicted value (7% change), an increase in BMI Z score of 0.3, and secondary outcomes of measures of gut health and function; an increase in plasma total fatty acids from 8.5 to 10.5 mmol/L, an increase in fecal elastase of 120 ug/g stool, and a decrease in fecal calprotectin (-30 ug/g stool change). Using STATA, power calculations were generated, with α =0.05, for paired data (n=16) within the same sample (before and after 12 weeks of treatment) using the changes described above for the primary outcomes and secondary outcomes.

Primary outcomes: A sample size of 16 subjects results in 86% power to see a decrease of 7% in **SEE** (i.e. from 115 to 108) with a standard deviation of the change of 9%, using a paired t-test two-sided significance level. We demonstrated a change of similar magnitude in REE in 24 subjects with CF gating mutation after 3-mo treatment with ivacaftor^{7,9}. For growth status, 16 subjects will provide 85% power to detect an increase in **BMI Z score** of 0.3 with a standard deviation of 0.4. In the KIWI study of 2 to 5 year old children with CFTR gating mutation treated with ivacaftor for 24 weeks, a BMIZ score increase of 0.4±0.4 was demonstrated⁶. We showed a BMI Z score increase over 12 weeks of 0.3±0.4 in our recent study of 18 children (5 to 19 years) with 12-week ivacaftor treatment⁷.

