Secondary outcomes: A sample of 16 subjects will provide 80% power to detect an increase in total plasma fatty acids from 8.5 to 10.5 mmol/L with a standard deviation of 2.8%, will provide 88% power to detect an increase in fecal elastase of 120 ug/g stool with a standard deviation of 150 ug/g stool, and will provide 85% power to detect a decrease in fecal calprotectin of 30 ug/g stool with a standard deviation of the change of 40 ug/g stool. We previously demonstrated a 3-month increase in plasma total fatty acids of this magnitude in subjects with CF receiving a fat-based nutritional supplement¹⁹. Davies et al⁶ demonstrated a change of 100 ug/g stool in fecal elastase with 24-week ivacaftor treatment in for 2 to 5 year old children with CFTR gating mutations in the KIWI study, and an even greater increase of 164 ug/g stool fecal elastase was shown in 1 to 2 year old children participating in the ARRIVAL study¹⁶. We have previously demonstrated a 3-month decrease of 30 ug/g stool in fecal calprotectin with ivacaftor treatment in 5 to 61 year old people with CFTR gating mutations⁷. The standard deviations of 9% for SEE, 40 ug/g stool for fecal calprotectin, 150 ug/g stool for fecal elastase and 0.4 for BMI Z score are reasonable estimates of the variability expected in changes for these variables from our experience with 3-12 month changes in these measures in previous longitudinal clinical trials we have conducted for changes in children and adults with CF^{7,18,19,37,38}. In addition, our recent experience with SEE measures in 1 year old healthy children showed a standard deviation of 8% in SEE percent predicted values³⁹ (personal communication).

We plan for up to 12% attrition over the 12 weeks. By enrolling 18 subjects we can account for attrition and also allow for the possibility of greater variability in the SEE, BMI Z scores and gut health and function measures.

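### Section 6.2 counts the same two spare places twice: at the planned 12% attrition, 18 enrolled leaves about 16 and no reserve for a larger standard deviation

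*Combined protocol and SAP*

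**What the plan says.** Section 6.2 fixes the target number: "The sample size of 16 subjects to complete the study has been determined as adequate". The calculations are described as being "for paired data (n=16) within the same sample (before and after 12 weeks of treatment"), at a 5% level, and for SEE the method is given as "using a paired t-test two-sided significance level". The two primary outcomes are a fall of 7 points in SEE percent predicted (SD of change 9, stated power 86%) and a rise of 0.3 in BMI Z (SD 0.4, stated power 85%).

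The same section closes with the allowance for losses, "We plan for up to 12% attrition over the 12 weeks", followed directly by the claim at issue: "By enrolling 18 subjects we can account for attrition and also allow for the possibility of greater variability in the SEE", and likewise in BMI Z and the gut measures.

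Section 3.2.2 says "Recruitment will stop when 18 subjects are enrolled" and expects those 18 to yield 16 evaluable subjects. It does not define evaluable.

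The path from enrolment to a usable pair has several steps. Sections 4.1 and 4.2 place written consent at Visit 1, ahead of any assessment. Section 7.1 says the study does not supply ivacaftor. Section 3.1.3 adds that "The exact date of the start of medication will vary for families", and that this may delay the 6-week visit. For SEE, the schedules for Visits 1 and 3 list "Day 3 (if needed and expected for half of subjects"), to be used when the test was not done on Day 2.

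**The concern.** The number 18 is given two jobs. It replaces children lost during treatment, and it protects the study if outcomes vary more than planned. Two spare places can do both only if few children are lost. At the attrition the plan itself allows for, replacing losses uses both places.

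This matters because both primary hypotheses rest on SDs taken from other settings: earlier studies by the group in children and adults with CF, and SEE in healthy one-year-olds. A reader who accepts the sentence in 6.2 will believe there is a cushion if those SDs prove too small in infants and toddlers with CF.

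The allowance for losses is also narrow. The 12% is stated for the 12 weeks, which section 3.1.3 counts from the start of ivacaftor, while recruitment closes on children enrolled. A child who is enrolled but never starts the drug, or who lacks a valid SEE at baseline or at 12 weeks, supplies no SEE pair, and 6.2 gives no separate allowance for such a child.

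**Working it through.** **Inputs (sections 6.2 and 3.2.2).** Completers needed: 16. Enrolled: 18. Attrition: up to 12%. Two-sided α = 0.05. SEE: difference 7, SD 9. BMI Z: difference 0.3, SD 0.4. The larger SDs used below (10 for SEE, 0.45 for BMI Z) are illustrative assumptions, since the documents name none.

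**1. Are the two spare places free?**
- Retained at the ceiling: 18 × (1 − 0.12) = 15.84, about 16.
- Enrolment needed for 16 at 12% loss: 16 / 0.88 = 18.2.
- Section 3.2.2 gives the same result: 18 to 16 is a loss of 2/18 = 11.1%.

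Attrition therefore accounts for both places. If each child is lost independently with probability 12%, the chance of keeping at least 16 of 18 is 63%.

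**2. The plan's own power figures at n = 16.** The normal approximation is Φ(δ√n/SD − 1.96).
- SEE: 7 × 4/9 = 3.111; Φ(1.151) = 87.5% (stated 86%).
- BMI Z: 0.3 × 4/0.4 = 3.0; Φ(1.04) = 85.1% (stated 85%).

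The stated figures lie close to this approximation. For the paired t-test that the plan names, power comes from the noncentral t distribution with n − 1 = 15 degrees of freedom, noncentrality δ√n/SD and critical value 2.131:
- SEE: 82.8%.
- BMI Z: 80.1%.

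So at 16 pairs BMI Z has essentially no margin above 80%. SEE keeps 80% power only up to an SD of 9.34.

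**3. Power by number of evaluable pairs and SD (exact two-sided paired t-test).**

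| Pairs | SEE, SD 9 | SEE, SD 10 | BMI Z, SD 0.40 | BMI Z, SD 0.45 |
|---|---|---|---|---|
| 14 | 76.7% | 67.8% | 73.7% | 63.6% |
| 15 | 80.0% | 71.3% | 77.1% | 67.1% |
| 16 | 82.8% | 74.5% | 80.1% | 70.3% |
| 18 | 87.5% | 79.9% | 85.0% | 76.0% |

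The row for 16 is the position at the planned attrition. The row for 18 is the best case, with no loss of any kind.

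**4. Losses outside the 12%.** The documents give no rate for children who never start ivacaftor or for missing SEE tests, so no expected number of pairs can be derived. The table shows the cost of each: for SEE at SD 9, losing one pair below 16 costs about 3 points of power (82.8% to 80.0%) and losing two costs about 6 (to 76.7%).

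**The case against.** The strongest reply is that 12% is a ceiling. If only one child or none is lost, 17 or 18 pairs remain and SEE power at SD 9 is 85.3% or 87.5%, so there is some room for a larger SD. This stands, and a reader who concluded that no reserve can ever exist would go too far. But the reserve depends on attrition staying below the planned allowance, and it is small: with all 18 retained, 80% power tolerates an SEE SD of about 9.99 and a BMI Z SD of about 0.428.

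Three other inferences are tempting, and the documents do not support them.

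- **That 18 is miscalculated.** 16/0.88 = 18.2, and 15 SEE pairs still give 80.0%. The number is reasonable for attrition alone; the added claim is what fails.
- **That replacement is ruled out.** The documents are silent on it. Closing recruitment at 18 enrolled has that effect unless something else is specified. Section 3.2.2 can also be read as allowing two losses of any kind from enrolment on, but those are the same two places.
- **That half the SEE tests will fail.** Day 3 is a second opportunity, and section 9.6 uses the one-half as a payment assumption. Neither is a failure rate, and the success rate on Day 3 is not given. Any specific reduced number of SEE pairs built on this would be guesswork.

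It is also fair to say that the mixed model in section 6.1.1 can use a child with incomplete visits. That softens the loss for the later analysis. It does not change the stated power, which is for the paired comparison of baseline with 12 weeks and needs both ends.

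**Conclusion.** The sentence in 6.2 is wrong as written. At the planned maximum attrition, 18 enrolled gives about the 16 on which all the power figures depend, and no places remain for greater variability. At 16 pairs, power under the named test is 82.8% for SEE and 80.1% for BMI Z, and an SD about 11% to 12.5% larger (10/9 and 0.45/0.40) lowers these to 74.5% and 70.3%. Below the ceiling a small conditional reserve exists, but full retention does not restore 80% for either outcome at those SDs.

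The same two places must also cover children who never start treatment or lack a valid SEE at either end. How many there will be cannot be judged from the documents.

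The double counting rests only on the plan's own figures. The size of the power loss rests on the two illustrative SDs and on the planned effects being correct. The defect lies in what the plan claims for 18, and the sample size itself need not change.

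**What to change.** In section 6.2:

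- Delete the clause saying that 18 also allows for greater variability. Say instead that the two extra places cover all losses, from any cause, up to about 12%, and leave no reserve for a larger SD at that rate.
- State the paired t-test power at 16 pairs (SEE 82.8%, BMI Z 80.1%), with a short sensitivity table over the number of evaluable pairs and over a larger SD for each primary outcome. For SEE at SD 9 the entries are 77%, 80%, 83% and 87% at 14, 15, 16 and 18 pairs. The table under the working can be used directly.

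In section 3.2.2, define evaluable as having a valid value at both baseline and 12 weeks, and count evaluable pairs separately for SEE and BMI Z, since a child without an SEE pair may still have a BMI Z pair.

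This is a change of wording with no added visits, children or data collection. The cost is a slightly less favourable stated power for both primary outcomes.

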7 STUDY MEDICATION (STUDY DEVICE OR OTHER STUDY INTERVENTION)

7.1 Description

This is an observational study of subjects who will be assessed before and after ivacaftor use. The study will not provide the ivacaftor to the subjects. It will be clinically prescribed by the subject's home CF care provider and the subject will not begin the ivacaftor treatment until after all Baseline (Visit 1) study visit procedures have been completed.

8 SAFETY MANAGEMENT

8.1 Clinical Adverse Events

Clinical adverse events (AEs) will be monitored throughout the study.

8.2 Adverse Event Reporting

Since the study procedures are not greater than minimal risk, SAEs are not expected. If any unanticipated problems related to the research involving risks to subjects or others happen during the course of this study (including SAEs) these will be reported to the IRB in accordance with CHOP IRB SOP 408: Unanticipated Problems Involving Risks to Subjects. AEs that are not serious but that are notable and could involve risks to subjects will be summarized in narrative or other format and submitted to the IRB at the time of continuing review.

9 STUDY ADMINISTRATION

9.1 Data Collection and Management

Data Management: The CHPS will work with the study team to create case report forms, set up REDcap database, and provide training for data entry and quality assurance. REDcap, a secure, web-based database, provides real time calculations, error detection and an automated export procedure for seamless data downloads to Excel, SAS and Stata. REDcap and all study computers are password protected and allow for storage of direct identifiers and de-identified data in a single database. Subjects will be assigned a unique identification number to insure confidentiality. Biological specimens are stored, identified using unique numbers in locked CHPS freezer. Routine backup to a secure server, including images of forms, the main study database, and files created for analysis, and analysis programs will be archived daily. Source documents will be stored in locked cabinets in secure research facilities with locked doors and security alarm with 24 hour security guard response.

We will establish a database to store study data using standard software (e.g. RedCap). The database will be designed to perform automatic computations, such as exact age based upon birth date and date of exam, and averaging anthropometric measures, which are recorded in triplicate. Reports containing the number of subjects enrolled and data entered for each subject are generated and reviewed each month by the PI. The PI, or study staff, will review all data collection forms on an ongoing basis for data completeness and accuracy as well as protocol compliance. Following data entry, all primary and

secondary endpoint data will be verified against original source documents. Data verification will be performed by someone other than the individual originally collecting and entering the data.

All subjects will be assigned a unique identification number that will be used to insure strict confidentiality. The databases are secured with password protection to insure confidentiality and security. The informatics manager receives only coded information which is entered into the database under those identification numbers. Electronic communication with outside collaborators involves only unidentifiable information. A master list containing PHI and subject ID number will be kept separate from the data forms and the database that will only have a study ID number. The master list will be on a separate password protected file on CHOP's secured server. All source documents including case report forms, laboratory results, and subject study binders will be kept in secured locations on the 14th floor of the Roberts Center for pediatric Research. The file cabinets and the study-specific room will be locked with access to study personnel only, and the outer hallway is also locked with limited access to CHOP research personnel.

Routine backup to the main study database, files created for analyses, and analysis programs will be completed. The main study database will be archived on a daily basis and stored on a CHOP secured server. The Informatics Core of the CHPS will create case report forms, set up the database in RedCap, and provide oversight for data entry and quality assurance for this study.

There is no set time for destroying the information that will be collected for this study.

9.2 Confidentiality

Medical history information will be obtained at baseline. All of the materials collected are for research purposes only, and data will be kept in strict confidence. No information will be given to anyone without permission from the subject or parent/guardian of the subject. This will be stated in the consent form. Confidentiality is assured by use of identification codes. All data, whether generated in the laboratory or at the bedside, will be identified with a identification code unique to the subject.

To maintain confidentiality, private health information will be collected, accessed and stored in accordance with Institutional policies and HIPAA guidelines, including the use of multilevel password protection and enforcement of system user privileges on the database. To minimize the risk of disclosure, all direct identifiers will be removed as soon as possible and codes will be substituted for personal identifiers. Records of individuals are stored with ID numbers and a code with no discernible personal identifiers. Code lists and data files will be stored in separate, secure locations. Data will be accessed and stored on password-protected computers on the CHOP network. To maintain confidentiality, codes will be used in the database, presentations and publications. The Investigator and other site personnel will not use such data and records for any purpose other than conducting the study.

9.3 Regulatory and Ethical Considerations

9.3.1 Data and Safety Monitoring Plan

Safety will be formerly monitored weekly by the study team and PI. The IRB and CHPS will also monitor safety. The study protocol will be carried out in accordance with OHRP and NIH guidelines and requirements. SAEs that are unanticipated, serious, and possibly related to the study will be reported to the IRB, CHPS, all members of the research team, the clinical care team, and sponsor in accordance with requirements.

9.3.2 Risk Assessment

There is minimal risk to the subject associated with delaying clinically prescribed ivacaftor treatment until all procedures for the baseline visit (Visit 1) have been completed.

The procedures in this study involve the potential risks related to the drawing of blood. The risks of drawing blood are rare, and minimal. There is a small risk of pain, infection and local irritation associated with the blood draw. However, this is considered a minimal risk and skilled pediatric research nursing staff will perform phlebotomy. Each subject will have approximately 18cc (approximately 1.2 tablespoons) of blood drawn at baseline (Visit 1) and 12 week (Visit 3) study visit, and 5 cc(1 teaspoon) at the 6 week visit (Visit 2), and no more than 5mL/kg over an eight week period.

The sleeping energy expenditure assessment using the metabolic cart poses minimal risk to the subjects. There is minimal risk associated with anthropometric measurements, sharing dietary intake, demographic information, health history and medical information.

Collection and storage of stool is associated with a small risk of fecal contamination. However, for safety and convenience, subjects will be provided with proper stool collection instructions and supplies (gloves, disposable collection containers, storage freezer container).

Private health information will be collected, accessed and stored according to HIPAA guidelines, including the use of multilevel password protection and enforcement of system user privileges on the database. To minimize the risk of disclosure, all direct identifiers will be removed as soon as possible and codes will be substituted for personal identifiers. Records of individuals are stored with ID numbers and a code with no discernible personal identifiers. Code lists and data files will be stored in separate, secure locations. Data will be accessed and stored on password-protected computers. To maintain confidentiality, codes will be used in the database, presentations and publications.

If clinically significant results are found as a results of this research study, subjects/families will be informed and consent to share findings with their clinical care team will be obtained. Once consent to share medical information is obtained, the subject's clinical care team will be contacted by the study team and the results transferred for appropriate follow-up.

In the event of a serious adverse event during the study protocol, it will be reported to [name] (Principal Investigator), the IRB and CHPS, all study team members and sponsor as directed by policies and procedures and in accordance with requirements. With the approval of families, the information will be provided to their care providers as directed.

9.3.3 Potential Benefits of Study Participation

We cannot ensure a direct benefit to the subjects or their families as a result of participating in this study. Participants and their families may benefit from knowing that they will contribute to a clinical research study that is important to the health of people with CF in the U.S. and around the world.

9.3.4 Risk-Benefit Assessment

The research we propose is justified, considering that the risk associated with participation is minimal compared to the potential and anticipated benefits. The benefits of participation clearly outweigh the risks, in view of the positive and long-lasting benefits of the study to the larger population of people living with CF.

9.4 Recruitment Strategy

It is expected that all subjects will be recruited by word of mouth and at the recommendation of the subjects' CF Care Team. The CF Foundation, CF Centers and CF support organizations around the country and Canada will provide the study with resources that will aide in recruitment efforts (i.e. to help to identify young subjects with "gating" mutations). Subjects will be recruited after introduction by the subject's CF Care Team. In this initial discussion of the study, we plan to have the subject's CF Care Team use the Family Recruitment Flyer, which leaves them with information about the study as well as contact information for the study team. The Family Recruitment Flyer will be used as a tool that explains the study in easier terminology, since the flyer sent to other CF Centers has a lot more complicated and confusing information that could potentially be overwhelming for families. The flyer explains to the family why they and their child are being recruited and what the purpose of the study is, and leaves the family with contact information for our study team if they want to reach out. Once a family has expressed interest in participating a CHOP-based research team member will contact the family via telephone or in person and continue the introduction of the study to families. Written (in person) or verbal (via phone) consent will be acquired to collect medical information to determine eligibility. For verbal screening consent, a waiver of documentation of consent, a waiver of assent and an alteration of HIPAA to obtain verbal consent and HIPAA authorization for screening over the phone will be in place. A waiver of verbal assent is requested due to the fact that the child is too young to provide it. In the event that a non-English speaking family is approached for screening, an interpreter will be used either by phone or in person depending upon whether the screening takes place verbally over the phone or in person to present the study in a language understandable to the subjects/families. The interpreter can be conferenced into the phone call for the consent process. The screening consent will include the Study Summary Document for interpreter documentation attesting to statements on the summary document. This document will be faxed or emailed (using secure email) to the interpreter to sign and sent back electronically if the process takes place by phone. All members of the team will be available to discuss the details and answer any study related questions as they arise. Once interest and eligibility are determined, procedures to set up enrollment will begin.
